8. REMOVAL OF PARTICIPANTS AND STUDY TERMINATION

8.1. Participant Withdrawal from the Study

Participant (or their legally authorized representative) may withdraw their consent to participate in the study at any time without prejudice. The physician must withdraw from the study any participant who requests to be withdrawn. Withdrawal from this study relates only to this study (and therefore the AbD) and does not impact follow-up of a participant in the DHR per local regulations.

Reasons for removal of a participant from the study include the following:

- Death
- Lost to follow-up (see Section 8.2)
- Use of any investigational product or investigational medical device during the study
- Participant was erroneously admitted into the study or does not meet entry criteria per Section 5.2.1
- Participant no longer has severe hemophilia A (eg, participant has received liver transplant)

The investigator or designee must explain to each participant, before enrollment into the study, that for the evaluation of study results, the participant's protected health information obtained during the study will be shared with the sponsor, regulatory agencies, and the IRB/IEC/REB. It is the physician's (or designee's) responsibility to obtain written permission to use protected health information per country-specific regulations, from each participant, or if appropriate, the participant's legally authorized representative. If permission to use protected health information is withdrawn, it is the investigator's responsibility to obtain a written request, to ensure that no further data will be collected from the participant and the participant will be removed from the study.

8.2. Lost to Follow-Up

It is not anticipated that participants will be lost to follow-up due to the routine clinical management of PwSHA, as well as data being collected consistent with ongoing disease management practices. However, a participant may be considered lost to follow-up if he repeatedly fails to attend visits at the study site or does not respond to attempts at contact made by the study site. A participant will be deemed lost to follow-up at the discretion of the participant's treating physician, as participants are expected to be seen consistent with routine clinical management. As PwSHA are expected to be seen at an HTC at least annually

(and likely every 6 months), a participant may be considered lost to follow-up if he has not been seen, or no data has been reported into the DHR (whichever is later) for 18 months. Before a participant is deemed lost to follow-up, the treating physician or designee should make every effort to regain contact with the participant.

For the purposes of analyses, a participant's follow-up will be censored at the end date of the most recent data entry period into the DHR. At the time of final data cut, any participant without data entered into the DHR over the full follow-up period of this AbD (index date + 3 years) will be considered lost to follow-up and similarly censored. In reporting participants lost to follow-up, participants deemed lost to follow-up at the discretion of the investigator will be reported separate from those considered lost to follow-up at the time of the final data cut.

8.3. Replacement of Participants

All participants consenting to the AbD data collection during the recruitment period (see Section 5.1) will be included in the study. Participants will not be replaced if lost to follow-up or withdrawn from the study as a replacement participant would not be followed for 3 years by the time that the AbD is due to complete ([AM-RL 2023](#)).

8.4. Study Termination

BioMarin (the sponsor) reserves the right to discontinue the study at any time. Premature termination of the study may occur because of a regulatory authority decision, a change in the opinion of the IRB/IEC/REB, clinical or safety reasons, or at the discretion of the sponsor. The sponsor reserves the right to discontinue participation by an individual investigator or site for poor enrollment or noncompliance. Any decision to terminate the study will be promptly communicated to study physicians, regulatory authorities, and the IRB/IEC/REB. The study physician is responsible for communicating any decision to terminate the study to hospital/HTC staff involved in the conduct of the study and the participating participants (and/or their legally authorized representative).

8.4.1. Futility Assessment

A futility analysis will be conducted at the 18-month interim analyses to assess whether the study should be terminated early due to the inability to meet the required sample size for comparative analyses. The futility analysis will examine the total number of participants enrolled in the study, the number of participants in the Roctavian Cohort and SoC Cohort at the time and the amount of time remaining in the participant recruitment window.

Assessments of potential futility and implications on study interpretation will be discussed in the reports associated with these interim analyses. Continued conduct of the study based on the futility assessment at these timepoints will be discussed with the G-BA.

A priori the sponsor would propose to discontinue the study if either of the conditions below were met (unless there is an indication that recruitment is expected to considerably increase during the remainder of the recruitment period):

- Roctavian Cohort is expected to include ≤ 33 persons (<50% of the target sample size for the Roctavian Cohort)
- SoC Cohort is expected to include <67 persons (target sample size of the Roctavian Cohort)

A futility assessment will also be included as part of the 36-month and 54-month interim analyses to determine the observed ABR of each cohort. The sample size calculation conducted a priori (see Section 10.1) will be re-calculated based on the observed ABR of each cohort at these timepoints. Implications on study interpretation will be discussed in the reports associated with these interim analyses. Continued conduct of the study as described in the original study protocol based on the futility assessment at these timepoints will be discussed with the G-BA.

Any changes to the conduct of the study and AbD based on the futility assessment will be made in agreement with the G-BA.

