10. STATISTICAL CONSIDERATIONS

10.1. Sample Size Determination

The primary goal of hemophilia treatment is to reduce the bleeding rate or to achieve freedom from bleeding. As an approximation of the appropriate number of cases for the data collection accompanying the application, the Institute for Quality and Efficiency in Health Care (IQWiG) conducted the sample size calculation based on ABR for treated bleeds. Evaluation of the ABR is performed using a negative binomial model. The relative effect measure is the incidence rate ratio of Roctavian over SoC, which can be tested against the shifted null hypothesis of 0.5, assuming a significance level $\alpha = 2.5\%$ with a one-sided test, and power of at least 80%. Higher values for the ABR (parameter λ) stand for a worse outcome. Furthermore, a distribution of the Sample Roctavian vs. SoC of 1:5 is assumed (sample size ratio $\theta = 0.2$). Other required parameters are the Average Exposure Time ($u_t = 1$ year), the ABR for the SoC and Roctavian groups ($\lambda_{\text{SoC}} = 3$, $\lambda_{\text{Roctavian}} = 0.85$) and a value for the overdispersion ($\phi = 1.5$). This results in a total sample size of at least 397 participants (Roctavian Cohort $n = 67$, SoC Cohort $n = 330$) ([Zhu 2017](#)).

Based on current estimates of participant enrollment, the study will be powered based on the ABR approach. The sample size calculation is based on a shifted null hypothesis to add robustness to the generated evidence. However, the actual null hypotheses for testing all primary and secondary endpoints are not shifted.

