7.6. Study Sample Size

The primary goal of HA treatment is to reduce the bleeding rate or to achieve freedom from bleeding. As an approximation of the appropriate number of cases for the data collection accompanying the application, the Institute for Quality and Efficiency in Health Care (IQWiG) conducted the sample size calculation based on ABR for treated bleeds. Evaluation of the ABR is performed using a negative binomial model.

The formula for The sample size calculation is as follows:

$$N_1 \geq \frac{(z_\alpha \sqrt{V_0} + z_\beta \sqrt{V_1})^2}{(\log(R_0) - \log(\lambda_2/\lambda_1))^2}$$

$$N_2 = \theta N_1$$

Where:

$$V_1 = \frac{1}{\mu_t} \left(\frac{1}{\lambda_1} + \frac{1}{\theta \lambda_2} \right) + \frac{(1 + \theta)\varphi}{\theta}$$

V_0 is computed using the fixed marginal total method, the 2nd method recommended by Zhu et al.:²⁷

$$V_{02} = \frac{(1 + R_0\theta)^2}{\mu_t R_0 \theta (\lambda_1 + \theta \lambda_2)} + \frac{(1 + \theta)\varphi}{\theta}$$

N_1 is the sample size for control, N_2 is the sample size for intervention. $\theta = \frac{N_2}{N_1}$, which is the sample size ratio; R_0 is the superiority margin ratio at the null hypothesis. In this case, R_0 is <1 since higher rates are worse. λ_1 is the event rate in the control group, and λ_2 is the event rate in the intervention group. φ is the dispersion parameter, and μ_t is the average exposure time. z_α is the z-score at the significance level, z_β is the z-score at the power value.

When higher rates are worse, the superiority by a margin test hypotheses are

$$H_0: \frac{\lambda_2}{\lambda_1} \geq R_0 \quad \text{vs.} \quad H_1: \frac{\lambda_2}{\lambda_1} < R_0$$

Where $R_0 < 1$.

The relative effect measure is the incidence rate ratio of Roctavian over SoC, which can be tested against the shifted null hypothesis of 0.5, assuming a significance level $\alpha = 2.5\%$ with a one-sided test, and power of at least 80%. Higher values for the ABR (parameter λ) stand for a worse outcome. Furthermore, a distribution of the Sample Roctavian vs. SoC of 1:5 is assumed (sample size ratio $\theta = 0.2$). Other required parameters are the Average Exposure Time ($u_t = 1$ year), the ABR for the SoC and Roctavian groups ($\lambda_{SoC} = 3$, $\lambda_{Roctavian} = 0.85$) and a value for the overdispersion ($\phi = 1.5$). This results in a total sample size of at least 397 participants (Roctavian Cohort $n = 67$, control Cohort $n = 330$).

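### The month-36 and month-54 futility recalculation uses a formula that is blind to which side of the 0.5 margin the observed rate ratio lies on, so above 0.5 the required sample size falls as the drug looks worse

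*Protocol*

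**What the plan says.** Section 8.4.1 sets two kinds of futility assessment. At month 18 it looks at recruitment and gives numeric discontinuation criteria: an expected Roctavian Cohort of 33 or fewer, or an expected SoC Cohort below 67. At months 36 and 54 it looks at bleeding rates: the a priori sample size calculation "will be re-calculated based on the observed ABR of each cohort at these timepoints". SAP 7.9.6.1 repeats this. Only the ABR is named as updated. No numeric criterion is given for these two timepoints; the implications go into the reports and continuation is discussed with the G-BA.

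The formula is printed in SAP 7.6, where R0 "is the superiority margin ratio at the null hypothesis" and the alternative is a ratio below R0. Section 10.1 gives the same inputs: an incidence rate ratio "which can be tested against the shifted null hypothesis of 0.5", one-sided 2.5%, power of at least 80%, ABRs of 3 and 0.85, 1 year of exposure, dispersion 1.5, allocation 0.2. The stated result is 330 + 67 = 397.

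Two other statements bear on this. Section 10.1 says that the null hypotheses actually tested are not shifted, whereas SAP 7.9.3 tests the primary rate ratio against 0.5. Section 5.1 plans 3 years of follow-up per participant.

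**The concern.** A sample size formula may square its effect distance when the planner chooses an effect on the correct side of the margin. An observed ratio carries no such guarantee. Once it exceeds 0.5, the squared distance grows as the drug looks worse, and the required sample size shrinks. A null or harmful result is what a futility check based on effect should expose, and there the recalculation can return a figure below the planned one. Neither 8.4.1 nor SAP 7.6 or 7.9.6.1 says what to do when the observed ratio is at or above the margin.

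There is also a question of relevance. By then the useful question is whether the participants already enrolled can still deliver a positive result, and a new required size does not answer that directly.

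**Working it through.** **Inputs** (Section 10.1, SAP 7.6): λ1 = 3 (SoC), λ2 = 0.85 (Roctavian), R0 = 0.5, θ = 0.2, φ = 1.5, μ = 1 year, z = 1.960 and 0.842.

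**Formula** (SAP 7.6, fixed marginal total variance under the null):
- V1 = (1/μ)(1/λ1 + 1/(θλ2)) + (1+θ)φ/θ
- V0 = (1+R0θ)² / (μR0θ(λ1+θλ2)) + (1+θ)φ/θ
- N1 = (1.960√V0 + 0.842√V1)² / (ln R0 − ln(λ2/λ1))², and N2 = θN1

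**Reproducing the plan.** V0 = 1.21/0.317 + 9 = 12.82. V1 = 0.333 + 5.882 + 9 = 15.22. The numerator is 106.1 and the denominator is (−0.693 + 1.261)² = 0.323. N1 = 328.8 and N2 = 65.8, so 329 + 66 against the printed 330 + 67. The formula is the one the plan used.

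**No effect, same SoC rate** (λ2 = 3). V0 = 1.21/0.36 + 9 = 12.36. V1 = 0.333 + 1.667 + 9 = 11.00. The numerator is 93.7 and the denominator is (−0.693)² = 0.480. N1 = 195.1 and N2 = 39.0, a total of 234 against 397 planned, or 41% lower.

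**Across observed ratios**, SoC ABR 3, 1 year of exposure, N1 to the nearest whole number:

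| Observed ratio | N1 (SoC) |
|---|---|
| 0.283 (design) | 329 |
| 0.40 | 2043 |
| 0.50 | unbounded |
| 0.60 | 2940 |
| 0.80 | 432 |
| 0.855 | 330 |
| 0.90 | 274 |
| 1.00 | 195 |
| 1.50 (harm) | 75 |

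N1 exceeds plan from just above the design ratio up to about 0.855 and is below plan beyond that.

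**Equal ABRs in both cohorts, 1 year.** N1 is 220 at a common ABR of 2, 291 at 1 and 329 at 0.79. Below about 0.79 it exceeds the planned 330.

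**What the enrolled sample could achieve at ratio 1.0.** With 330 + 67, the standard error of the log ratio is √[(1/3+1.5)/330 + (1/3+1.5)/67] = 0.181. The chance that the upper 95% limit falls below 0.5 is Φ(−0.693/0.181 − 1.96), about 4 × 10⁻⁹. The formula returns 195 + 39 for the same situation.

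**Exposure, a separate matter.** At the design rates N1 is 329 at 1 year, 275 at 2 years and 256 at 3 years; 328.8/255.7 = 1.29, so holding 1 year overstates the size by about 29% relative to 3 years. At equal ABRs of 3, N1 is 195 at 1 year and 163 at 3 years.

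**The case against.** The strongest reply is that there is no decision rule here to go wrong. Numeric discontinuation criteria exist for month 18 only. At months 36 and 54 the recalculated size goes into a report that also carries the cohort ABRs and the comparative results, so a ratio near 1 would be in plain view, and any change needs the G-BA's agreement. This stands. A reader might infer that the study would be declared adequately sized and continued in error; the documents set no threshold that would produce that outcome.

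A second reply is that SAP 7.6 states the formula for ratios below R0, so evaluating it at 1.0 is misuse. That is true of the formula, but 8.4.1 prescribes inserting whatever ABRs are observed and provides no guard.

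Third, a reader might infer that any drug with no effect returns a smaller size. It does not: ratios from 0.5 to about 0.855 return a larger one, and equal ABRs below about 0.79 do too (at 1 year of exposure). For partial effects the recalculation does warn.

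Fourth, a reader might blame the fixed 1-year exposure for the small figure at no effect. It works the other way (195 at 1 year, 163 at 3). That exposure and dispersion stay fixed is itself inferred from the ABR being the only input named. Three years is also an upper bound: with data cut 4 to 6 months before the report (Section 10.4), follow-up at month 36 is at most 30 to 32 months.

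Fifth, it is tempting to say that recruitment will certainly have closed. The synopsis dates point that way, but Section 5.1 lets the window move with the G-BA deadlines, and Section 8.3 ("Participants will not be replaced if lost to follow-up or withdrawn from the study") concerns replacement, not closure.

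Finally, one might want every ratio at or above 0.5 to count as futile. That presumes the 0.5 null, which Section 10.1 says is not the one tested. With 330 + 67, 3 years of exposure and dispersion 1.5, a true ratio of 0.6 has about 84% power against a null of 1: the standard error is √[(1/9+1.5)/330 + (1/5.4+1.5)/67] = 0.173, and 0.511/0.173 − 1.96 = 0.99.

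**Conclusion.** The point holds as a defect in a stated method. The recalculation is valid only when the observed ratio is below 0.5. Above it, the required size falls as the drug looks worse, and at an SoC ABR of 3 with 1 year of exposure it drops below the planned 330 SoC participants from a ratio of about 0.855, reaching 195 at no effect and 75 at a 50% excess of bleeds. With equal ABRs it falls below plan only when the common ABR is about 0.79 or more. These figures assume dispersion 1.5 and allocation 0.2 as designed.

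The consequence is a misleading number in the month-36 and month-54 reports. The final estimate and the type I error are untouched. The exposure mismatch is a second, smaller fault in the opposite direction, and it is conditional on exposure being left at 1 year. The change should be made, but the study does not fail without it.

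**What to change.** In Section 8.4.1 and SAP 7.9.6.1:

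1. Replace the recalculation, or accompany it, with conditional or predictive power for the enrolled sample, using the observed rate ratio and its standard error, the observed dispersion, and the accrued plus remaining exposure.
2. Compute that power against the null hypothesis that will actually be tested. This requires Section 10.1 (null not shifted) and SAP 7.9.3 (null of 0.5) to be reconciled first.
3. If the recalculated size is kept, state that it is not interpretable when the observed ratio is at or above the margin, and say which exposure and dispersion values enter it.
4. Do not add an automatic rule that a ratio at or above the margin is futile.

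The cost is a wording change in both documents and one short extra calculation per interim report.

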9. SAFETY DATA COLLECTION, RECORDING AND REPORTING

Secondary use of data in observational research means that there is no potential to collect individual serious and non-serious adverse events (AEs), pregnancy exposures, or incidents related to BioMarin products during the conduct of this research as the minimum criteria needed to report AEs, pregnancy exposures, and incidents may not be recorded in the data source (ie, AbD).

Therefore, the reporting of adverse drug reactions (ADRs) in the form of individual case safety reports will not be performed for data extracted from the DHR (GVP VI.C.1.2.1.b). It is assumed that reporting of corresponding safety data extracted/analyzed as part of this study has been appropriately performed in accordance with local requirements and documented at the time these data were collected through primary data collection mechanisms. Monitoring of safety data via routine on-site and remote monitoring visits (see Section 11.8) will be utilized to ensure that relevant targeted AEs are reported to the study sponsor for participants in this study consistent with local practice.

9.1. Local Requirement for Reporting of Safety Events

In Germany, physicians are obliged to report unintended drug reactions (unerwünschte Arzneimittelwirkungen) coming to their attention in the context of their therapeutic activity to the Drug Commission of the German Medical Profession (Arzneimittelkommission der deutschen Ärzteschaft, specialist committee of the German Medical Association) and incidents relating to the use of medicinal products and devices to the relevant competent authority ([Model Professional Code for Physicians in Germany - MBO-Ä 1997](#)).

10. STATISTICAL CONSIDERATIONS

10.1. Sample Size Determination

The primary goal of hemophilia treatment is to reduce the bleeding rate or to achieve freedom from bleeding. As an approximation of the appropriate number of cases for the data collection accompanying the application, the Institute for Quality and Efficiency in Health Care (IQWiG) conducted the sample size calculation based on ABR for treated bleeds. Evaluation of the ABR is performed using a negative binomial model. The relative effect measure is the incidence rate ratio of Roctavian over SoC, which can be tested against the shifted null hypothesis of 0.5, assuming a significance level $\alpha = 2.5\%$ with a one-sided test, and power of at least 80%. Higher values for the ABR (parameter λ) stand for a worse outcome. Furthermore, a distribution of the Sample Roctavian vs. SoC of 1:5 is assumed (sample size ratio $\theta = 0.2$). Other required parameters are the Average Exposure Time ($u_t = 1$ year), the ABR for the SoC and Roctavian groups ($\lambda_{\text{SoC}} = 3$, $\lambda_{\text{Roctavian}} = 0.85$) and a value for the overdispersion ($\phi = 1.5$). This results in a total sample size of at least 397 participants (Roctavian Cohort $n = 67$, SoC Cohort $n = 330$) ([Zhu 2017](#)).

Based on current estimates of participant enrollment, the study will be powered based on the ABR approach. The sample size calculation is based on a shifted null hypothesis to add robustness to the generated evidence. However, the actual null hypotheses for testing all primary and secondary endpoints are not shifted.

10.2. Populations for Analysis

All participants who consent to participate in this study and fulfill the inclusion/exclusion criteria (see Section 5.2) will be described, though the population analyzed may differ from the overall population if data is missing for a variable required for a specific analysis. Minimal missing data is expected as most fields required for the analysis in the DHR are mandatory and data monitoring (see Section 7.1.2) will ensure timely and completeness of data entry for all relevant fields.

For specific analyses, the population included will be required to have data collected for the outcome of interest required for the analysis (eg, participants with a missing Haemo-QoL-A score at baseline would be excluded from an analysis of change from baseline in Haemo-QoL-A or a comparison of participants achieving the minimal clinically important differences [MCID] for the Haemo-QoL-A). *A priori* requirements for analyses are detailed further in the SAP, as for certain analyses the absence of an event (eg, bleed events) are not considered missing. The population not included in an analysis due to missing data will be described if ≥ 10 participants in each study cohort are excluded. Additional requirements/exclusions for specific analyses based on observations in the data (notably after the initial data cut for the first interim analysis) will be documented in the SAP and described in reports.

The cohorts for comparison in this study include:

- **Roctavian Cohort:** PwSHA without a history of or current inhibitors administered Roctavian during the study recruitment period.
- **SoC Cohort:** PwSHA without a history of or current inhibitors treated with exogenous FVIII replacement therapies or emicizumab and not administered Roctavian during the study recruitment period.

10.3. Statistical Analysis

The SAP will be finalized prior to the initial data cut to complete the 18-month interim analysis. A draft of the SAP including more technical and detailed description of the statistical analyses described in this section has been completed in conjunction with this protocol. This section is a summary of the planned statistical analyses of the most important endpoints, including primary and key secondary endpoints.

